14. OTHER ENDPOINTS AND ADDITIONAL REPORTING

Other endpoints evaluated for the PP, mITT, and AT populations are described below:

- **Evidence of ischemic biliary complications diagnosed within 6 months and within 12 months post-transplant:**
Ischemic biliary complications diagnosed within 6 and 12 months post-transplant will be summarized by prevalence (subject-based) and event-rates (per patient-year). The ratio of event rates between treatment groups (OCS/Control) will also be reported. Treatments will be compared statistically using a chi-square test for prevalence of events (subject-based) and Poisson regression (PROC GENMOD) for event-rates. Statistical significance will be demonstrated if the p-value is less than 0.05. A 95% confidence interval will be presented for the ratio of event rates (OCS/Control).
- **Evidence of non-ischemic biliary complications diagnosed within 30 days and within 6 months post-transplant:**
Exploratory analyses for the incidence of non-ischemic biliary complications within 30 days and within 6 months post-transplant will be analyzed in a manner similar to the above analysis for ischemic biliary complications. Non-ischemic biliary complications will be defined based on MedDRA Lowest Level Term (LLT) category.
- **Extent of reperfusion syndrome as assessed based on the rate of decrease of lactate over the following time points:**
 - During a hepatic phase immediately before reperfusion of the transplanted liver
 - 30-40 minutes after hepatic artery and portal vein reperfusion of the transplanted liver
 - 90-120 minutes after reperfusion of the transplanted liver

The reperfusion rate will be estimated for transplanted recipients with a measurement prior to reperfusion of the transplanted liver and at least one of the two additional timepoints. The per-subject slope will be estimated using linear regression modeling across the timepoints. Reperfusion syndrome is defined as a slope > 0 . Subjects with a slope less than or equal to 0 will be classified as not having reperfusion syndrome.

Reperfusion syndrome will be summarized by prevalence (subject-based). Treatments will be compared statistically using a chi-square test for prevalence of events, with statistical significance demonstrated if the p-value is less than 0.05. A 95% confidence interval will be presented for the difference in prevalence (OCS – Control).

- **Average pathology sample score (single score per liver) for liver tissue samples as defined in the protocol taken at the following time points (applies to both OCS and Control arms):**
 - Donor liver pre-retrieval
 - Post-OCS and Control preservation at the end of back preparation and immediately before the start of re-implantation

- 90-120 minutes after reperfusion of the transplanted liver

Average pathology sample score will be summarized by treatment group using descriptive statistics. The difference in means between treatment groups will also be reported. 95% confidence intervals based on the t-distribution will be presented for the true means for each treatment and for the true difference in means between treatments (OCS – Control). Treatments will be compared statistically using a two-sided, two-sample t-test. Statistical significance will be demonstrated if the p-value is less than 0.05.

Additional evaluations for the PP, mITT, AT, mITT2, and ITT populations are described below:

- **Follow-up status**

For the PP, mITT, and AT Populations subject and liver graft status will be reported at the 30 day, 6 month, 12 month, and 24 month visits. Subject survival and liver graft survival will be tabulated by treatment group at each follow-up visit using counts and percentages. The number of subjects with liver graft related re-hospitalization between the 30 day and 6 month follow-up visits and between the 6 month and 12 month follow-up visits will be summarized using counts and percentages.

Kaplan-Meier estimated probabilities of recipient survival and liver graft survival will be presented for the PP, mITT, and AT Populations at the following nominal timepoints: 30 days, 6 months, 12 months, and 24 months post-transplantation.

Recipient and liver graft status will be reported at 30 days post-transplant for the mITT2 and ITT populations.

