4.3. Other Endpoints

- Length of initial post-transplant ICU stay
- Length of initial post-transplant hospital stay
- Evidence of ischemic biliary complications diagnosed at 6 and at 12 months post-transplant
- Extent of reperfusion syndrome as assessed based on the rate of decrease of lactate over the following time points:
 - During anhepatic phase immediately before reperfusion of the transplanted liver
 - 30-40 minutes after hepatic artery and portal vein reperfusion of the transplanted liver
 - 90-120 minutes after reperfusion of the transplanted liver
- Pathology sample score for liver tissue samples taken at the following time points (applies to both OCS and Control arms):
 - Donor liver pre-retrieval
 - Post-OCS and Control preservation at the end of back preparation and immediately before the start of re-implantation
 - 90-120 minutes after reperfusion of the transplanted liver

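### The lactate endpoint is titled as an extent and a rate of decrease, but SAP section 14 compares only whether each subject's slope is above zero

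*SAP*

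**What the plan says.** Protocol section 4.3 (and the synopsis) lists the endpoint as "Extent of reperfusion syndrome as assessed based on the rate of decrease of lactate over the following time points". The time points are one sample just before reperfusion, one at 30-40 minutes after it and one at 90-120 minutes. The protocol gives no cut-off, and its section 9 gives no analysis for this endpoint.

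SAP section 14 repeats the title and then sets out these steps:

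- A subject is evaluable "with a measurement prior to reperfusion of the transplanted liver and at least one of the two additional timepoints", so each slope rests on two or three readings.
- "The per-subject slope will be estimated using linear regression modeling across the timepoints".
- "Reperfusion syndrome is defined as a slope > 0". For all the others, "Subjects with a slope less than or equal to 0 will be classified as not having reperfusion syndrome".
- Prevalence is reported by arm and compared by a "chi-square test for prevalence of events, with statistical significance demonstrated if the p-value is less than 0.05". A 95% confidence interval is given for the OCS - Control difference in prevalence.

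No mean, median or between-arm comparison of the slope is planned. The titles of SAP Tables 2.4.1 to 2.4.3 list only reperfusion syndrome for this item.

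**The concern.** Extent and rate of decrease are quantities. The planned result is the proportion of subjects whose fitted lactate trend rises. Among subjects whose lactate falls, the speed of the fall, which is what the title names, has no effect on the result. Near zero the reverse happens: a slightly positive and a slightly negative slope, some of them fitted to two readings, are counted as opposite outcomes.

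At stake is whether the trial reports the endpoint it names. If OCS livers clear lactate faster or more slowly than Control livers, but few subjects in either arm have a rising trend, the planned table could show no difference. The slopes that would show one have already been computed.

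**Working it through.** The plan states no sample size, power, prevalence, slope mean or SD for this endpoint, so there is no figure to reproduce. The check has three parts.

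**1. Title against analysis.**

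| Element | Protocol 4.3 | SAP 14 |
|---|---|---|
| Quantity named | Extent, from rate of lactate decrease | Same title |
| Quantity derived | Not specified | Slope per subject |
| Quantity compared | Not specified | Proportion with slope > 0 |

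The continuous quantity is computed and then dropped before any comparison. The next endpoint in the same section is treated differently: "Average pathology sample score will be summarized by treatment group using descriptive statistics", with a difference in means, 95% confidence intervals and a two-sample t-test. The SAP gives no reason for the different treatment.

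**2. Can the sign recover the rate?** Take two invented arms with normal slopes, in arbitrary units: mean -1 with SD 0.3, and mean -2 with SD 0.6. The probability of a positive slope is 1 - Φ(1/0.3) = 1 - Φ(3.33) = 0.04% in the first, and 1 - Φ(2/0.6) = 1 - Φ(3.33) = 0.04% in the second. The prevalences are identical, although one arm clears lactate twice as fast. The planned comparison therefore cannot stand in for the rate.

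**3. Illustration of the information kept.** Assume normal slopes, equal SD and a pure shift between arms. Let p be the proportion of slopes above zero and z the matching normal quantile. The efficiency of the sign relative to the mean slope is φ(z)² / [p(1 - p)]:

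- p = 50%: 0.3989² / 0.25 = 0.637
- p = 20%: 0.2800² / 0.16 = 0.490
- p = 10%: 0.1755² / 0.09 = 0.342

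Under this model the value falls below one half when p is below about 21% (or above about 79%).

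The result depends on the assumed shape. For double-exponential slopes with scale b, the variance is 2b² and the density at the cut-off is p/b for p up to 50%. The efficiency is then (p/b)² × 2b² / [p(1 - p)] = 2p/(1 - p).

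| Slopes above zero (assumed) | Normal slopes | Double-exponential slopes |
|---|---|---|
| 50% | 0.64 | 2.00 |
| 20% | 0.49 | 0.50 |
| 10% | 0.34 | 0.22 |

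The two models agree at 20%. At 50% they point in opposite directions: the second makes the sign the more efficient analysis. The documents do not say which row or column applies.

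**The case against.** The SAP rule is explicit and complete: it fixes who is evaluable, the cut-off, the handling of a zero slope, the test and the interval. A syndrome can reasonably be defined as present or absent, and the protocol leaves room in how it is to be assessed. All this stands, and it is why the prevalence can stay in the tables. It does not answer the point that the title promises extent and rate while only presence is compared. SAP section 5.1 puts all collected data in listings, but a listing is not a comparison between arms.

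A reader might infer two stronger criticisms that the documents do not support.

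- **That the rule discards most of the information and has much lower power.** This needs a prevalence and a distribution, and the documents give neither. Even with normal slopes the loss exceeds half only when positive slopes are uncommon or very common. With a heavier-tailed shape the sign can do better than the mean. Slopes from two readings and from three also differ in precision, which makes a single normal distribution doubtful.
- **That the SAP departed from a prespecified method without listing it in section 3.5.** SAP section 1 undertakes to explain changes from the statistical methods in the protocol. The protocol gives no method for this endpoint and defers to a formal SAP in its section 9.9. The SAP filled a gap. The mismatch is with the endpoint's definition, not with a planned test.

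It can also be said that a t-test on slopes gives a noisy two-reading slope the same weight as a three-reading one. That is fair, and the choice of model should allow for it.

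**Conclusion.** The point holds in this form: SAP section 14 computes a lactate slope per subject but compares only its sign, so neither the extent nor the rate of decrease named in the title is compared between arms. That follows from the text and needs no assumption.

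The statistical cost is not established. The 64%, 49% and 34% figures illustrate one model (normal slopes, equal SD, shift between arms) at assumed prevalences of 50%, 20% and 10%, and should be cited only with those conditions.

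Severity is minor. This is an other endpoint with no power target, outside the primary analysis and the fixed sequence of secondary tests, and no main conclusion of the trial depends on it.

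**What to change.** In SAP section 14 and Tables 2.4.1 to 2.4.3:

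1. Analyse the per-subject lactate slope by arm: mean and median, and the OCS - Control difference with a 95% confidence interval.
2. Test the difference with a two-sample t-test on the slopes or, preferably, a mixed model of lactate on time by arm, which also handles subjects with two rather than three readings.
3. State whether time is the actual or the nominal sampling time. The sign of a two-reading slope does not depend on this, but its size does.
4. Keep the prevalence of slope > 0, with its chi-square test and interval, as a supplementary result.

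The cost is about a paragraph of SAP text and added rows in three tables. The slopes are already computed and no new data are needed. The downside is one more analysis of a low-ranking endpoint.

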APPENDIX 1. LIVER TISSUE BIOPSY, BILE DUCT SPECIMEN, & SCORING PROTOCOL

Liver Parenchyma Tissue Sample:

- Each tissue specimen is a 2.0 cm long 16-gauge needle biopsy taken perpendicular to the liver capsule from the right lobe. It should be stressed that the needle NOT be inserted parallel to the capsule.
- The tissue sample can then be placed in 10% neutral-buffered formalin, which is standard at most institutions.
- The specimen container must be CLEARLY LABELED with an anonymous code and specimen information. Bar coding is preferable.
- The label should also contain the timing of the biopsy: a) donor pre-retrieval; b) post-preservation (before implant); and c) post-reperfusion.

Timing of Liver Biopsy Samples:

- Liver tissue samples taken at the following time points:
 - Donor liver pre-retrieval. Only donor livers that are clinically suspected to be fatty by retrieval team visualization, will require a pre-retrieval biopsy readout to estimate the degree of macrosteatosis and confirm eligibility ($\leq 40\%$ macrosteatosis)
 - Post-OCS and Control preservation at the end of back preparation and immediately before the start of re-implantation
 - 90-120 minutes after reperfusion of the transplanted liver (prior to abdominal closure)

Bile Duct Specimens (if applicable):

- Any tissue trimmed from the bile duct or cystic duct should be placed into 10% neutral buffered formalin, as above, and CLEARLY LABELED, as to the center and participant and location of the sample. For example, 001-001 "distal common bile duct trimming."

Timing of Bile Duct Specimen:

- Pathology sample of common bile duct taken post preservation (applies to both OCS and control arms).
 - Post preservation at the end of back preparation and immediately before the start of re-implantation OR
 - Post reperfusion-Prior to biliary anastomosis

Refer to core lab collection manual in the PROTECT Study Manual

Score

PARENCHYMAL CHANGES:

Total biopsy length: _____ mm Total number of portal tracts: _____ Biopsy Adequate: Yes No

Overall architectural integrity: normal/intact mild moderate severe distortion

1. Lobular necrosis:

1.1 Overall severity:	 NONE	 MILD	 MOD	 SEV	 N/A
1.2 Primary location:	 Periportal	 Midzonal	 Perivenular	 Panlobular	 NA

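### SAP Section 14 treats the pre-retrieval biopsy as a pathology outcome instead of using it as the same liver's baseline

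*SAP*

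**What the plan says.** SAP Section 14 describes the endpoint as "Average pathology sample score (single score per liver) for liver tissue samples as defined in the protocol taken at the following time points". Three samples follow: "Donor liver pre-retrieval", after preservation just before implantation, and 90-120 minutes after reperfusion. The analysis gives descriptive statistics and t-based confidence intervals. It adds that "The difference in means between treatment groups will also be reported", that "Treatments will be compared statistically using a two-sided, two-sample t-test", and that "Statistical significance will be demonstrated if the p-value is less than 0.05". It specifies no covariate, no change from baseline and no repeated-measures model. The results are reported for the PP, mITT and AT populations.

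Protocol Section 4.3 lists the endpoint as "Pathology sample score for liver tissue samples taken at the following time points (applies to both OCS and Control arms") and gives no further definition. Protocol Section 6.3 has a needle biopsy taken from every donor liver around cross clamp, but requires a pre-retrieval readout only when the retrieval team suspects a fatty liver.

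SAP Section 5.2 rules out covariate adjustment for the primary and secondary endpoints. It is silent on the other endpoints.

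The scoring form is in the Protocol, "APPENDIX 1. LIVER TISSUE BIOPSY, BILE DUCT SPECIMEN, & SCORING PROTOCOL". Its parenchymal part has graded items such as "Overall architectural integrity: normal/intact mild moderate severe distortion", locations and cell types to tick, and a percentage of sinusoids covered.

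**The concern.** The question is what preservation does to the liver. Donor livers differ before preservation starts, and the trial deliberately enrols older, DCD and steatotic donors. The pre-retrieval biopsy measures that starting point in the same organ. Comparing it between arms as an outcome cannot inform on preservation. Averaging it with the later samples pulls the arm difference toward zero. Leaving it out of the model for the later samples keeps between-donor variation in the error term and any baseline imbalance in the estimate.

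The same SAP section handles reperfusion lactate differently: a measurement before reperfusion is required, and it anchors the per-subject slope. The pathology analysis has no such anchor.

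At stake are the precision and clarity of a descriptive histology result, not the trial's main claim.

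**Working it through.** The documents give no SD, expected difference, power or score range for this endpoint, so there is no stated figure to reproduce. The check compares the texts and then illustrates the size in SD units.

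**1. Is the sample a usable baseline?** Protocol Section 6.3 places the biopsy in the donor, before OCS instrumentation or cold storage. The recipient may already have been randomized, because Protocol Section 9.5 randomizes once a matching liver is identified. The preservation method has still not acted on the tissue. SAP Section 5.2 does not bar this use.

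**2. What is tested?** There is one sentence on one t-test, a list of three samples, and the words average and single score per liver. Two readings fit:
- (a) one score per sample and a test at each time point;
- (b) one number per liver, averaged over the three samples, and one test.

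Under (a), the pre-retrieval comparison carries no information on preservation. Steps 3 and 4 size the other consequences.

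**3. Reading (b): dilution.** If preservation shifts both later samples by d and the first by 0, the mean of three shifts by (0 + d + d)/3 = 2d/3. For d = 0.3 SD (assumed) this is 0.2 SD.

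Inputs: 300 transplanted subjects at 1:1 (SAP Sections 3.1 and 3.2), so about 150 per arm; two-sided 0.05; equal variances and a common correlation ρ between samples (assumed 0.3 to 0.7); complete data. Power = Φ(effect / (s√(2/150)) − 1.96), with √(2/150) = 0.1155. The values of s² are:
- mean of three: (1 + 2ρ)/3
- mean of the two later samples: (1 + ρ)/2
- the same with ANCOVA: (1 + ρ)/2 − ρ²

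| ρ | Mean of three, t-test (0.2 SD) | Mean of two later, t-test (0.3 SD) | Mean of two later, ANCOVA (0.3 SD) |
|---|---|---|---|
| 0.3 | 66.0% | 89.7% | 93.5% |
| 0.5 | 56.4% | 85.1% | 95.7% |
| 0.7 | 49.1% | 80.5% | 99.1% |

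**4. One later sample: gain from adjusting.** The residual variance factor is 1 − ρ² and the SE ratio is √(1 − ρ²). The difference detectable with 80% power is (1.960 + 0.842) × 0.1155 × SE ratio.

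| Analysis | Variance removed | SE ratio | Detectable difference | Power for 0.3 SD |
|---|---|---|---|---|
| t-test | 0% | 1 | 0.323 SD | 73.8% |
| ANCOVA, ρ = 0.3 | 9% | 0.954 | 0.309 SD | 77.7% |
| ANCOVA, ρ = 0.5 | 25% | 0.866 | 0.280 SD | 85.1% |
| ANCOVA, ρ = 0.7 | 49% | 0.714 | 0.231 SD | 95.3% |

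A simple change score is a weaker remedy. Its SE ratio is √(2 − 2ρ) = 1.183, 1.000 and 0.775, worse than no adjustment at ρ = 0.3.

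**5. Baseline imbalance.** By chance alone, the pre-retrieval means of two arms of 150 can differ by up to 1.96 × 0.1155 = 0.23 SD either way (95% range). Unadjusted, a share ρ of this passes into the later comparison: 0.5 × 0.23 ≈ 0.11 SD at ρ = 0.5.

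**6. Secondary check: the score itself.** As the documents read, the parenchymal grades in Appendix 1 have no numeric codes, and there is no choice of items, weighting, direction or total. Higher is worse for necrosis and better for sinusoidal coverage. The bile duct items carry numbers, but that specimen is optional and is not taken before retrieval. Two invented livers, with grades coded 0-3 by assumption, show why the rule matters:
- Liver C: necrosis 1, inflammation 1, steatosis 2.
- Liver D: necrosis 2, inflammation 1, steatosis 0.

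Summing all three items gives C = 4 and D = 3. Leaving out steatosis gives C = 2 and D = 3. The maximum gives 2 and 2. The order depends on an unstated rule.

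**The case against.** - **The number of tests is not stated.** A reader might infer that one of three significance tests is spent on a pre-treatment sample. The SAP never says that a test is run at each time point, so that count is one reading only. The objection stands; the baseline point holds under either reading.
- **The unadjusted t-test is a valid test, and adjustment is about efficiency.** This largely stands. The analysis sets contain only transplanted subjects, non-transplanted subjects are re-randomized as new, and SAP Section 3.5 counts 43 transplanted off-study. Baseline differences therefore need not be chance alone, but the documents show no actual imbalance.
- **The SAP may not claim a protocol-defined score.** A reader might infer that it cites a definition that does not exist. The reference to the protocol directly follows the tissue samples, and the protocol does define those and their timing.
- **The scoring detail may lie elsewhere.** Some top-category codes in the bile duct list appear to have been lost in reading the form. A core-lab collection manual is cited but not included, and the draft case report forms are blank here. The finding is that no combining rule appears in these documents, not that none exists.
- **Bias from open-label scoring.** A reader might infer that the rule could be chosen with knowledge of the arms. Specimens carry an anonymous code, arm is not among the listed label contents, and the SAP is to be final before database lock. The documents do not support that inference.
- **Baseline scores may be incomplete.** Collection is planned for all donors, but an immediate readout is not. The Appendix 2 donor schedule has an explicit row only for the post-preservation biopsy, though its general donor liver assessment row may cover the earlier one. This is a real limit and belongs in the fix.

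**Conclusion.** The point holds. The plan collects a pre-treatment measurement of each liver and then analyses it as an outcome, where it is uninformative if tested alone and dilutes any effect if averaged in. Under the averaging reading the effect shrinks by one third, whatever its size, if preservation affects both later samples equally.

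The precision gain is uncertain. The 9%, 25% and 49% figures rest on assumed correlations, a linear model and complete baselines. Coarse grades with most livers in the lowest category would push the gain toward the low end, and missing baselines would reduce it further.

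The missing combining rule is a secondary matter of specification. The documents do not settle which items should form the score.

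The importance is low to moderate. This is an 'other' endpoint outside the fixed testing sequence, and neither the primary conclusion nor the sample size depends on it.

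**What to change.** Amend SAP Section 14 as follows, before core-lab data are opened:

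- Compare the arms on the post-preservation and post-reperfusion scores with a linear model (ANCOVA) adjusted for that liver's pre-retrieval score. State whether the two samples are analysed separately or as their mean.
- Keep the pre-retrieval sample out of any average. Report it by arm descriptively, without a between-arm test.
- State that the core lab scores every pre-retrieval sample, and how missing baselines are handled. One option is a single fill-in value common to both arms plus a missingness indicator.
- State or cite the coding, the items used, their direction, the treatment of not-applicable entries and the combining rule. Say what the average runs over. Which items to use is the sponsor's choice.

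The cost is SAP wording, plus confirming that all pre-retrieval samples are scored. They are already listed as endpoint samples, so no new biopsy is needed and enrolment does not change.

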Primary non-function rate	0 (0)	0 (0)
Early Allograft Dysfunction, n (%)	3 (15%)	9 (22.5%)
Peak AST within 7 days, (IU/L), median (range)	417 (84-4681)	902 (218-8786)
Initial Post-Tx. ICU stay (days), median (range)	3 (1-8)	3 (1-41)
Hospital Stay (days), median (range)	12 (6-34)	14 (8-88)

[figure not shown]
Source: Rising Star Symposium, International Liver Transplant Society, June 5, 2014, London, England; Abstract O-1, Human Liver Transplantation Using Normothermic Machine Preservation, Friend P, et al.
Sunrise Symposia; New Dimensions in Liver Transplantation, World Transplant Congress, July 31, 2014, San Francisco, CA, U.S.A.; Normothermic Machine Preservation of the Liver, Friend P, et al.

Based on the above overwhelming supportive pre-clinical, scientific and clinical evidence of safety, feasibility and potential benefits of warm machine perfusion for liver transplantation using identical perfusion protocols/perfusates to the OCS liver technology, we are proposing to proceed with a pivotal prospective clinical investigation of the OCS liver technology to compare its outcomes to cold static storage in liver transplant recipients.

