7.3. Long Term Follow-up: 6 and 12 & 24 months

Follow-up data collection will be conducted at approximately 6, 12, and at 24 months post-transplant.

7.3.1. 6 and 12-Month Follow-up

At approximately 6 and 12 months post-transplant, the patient will be evaluated at an office visit if this is the institution's standard of care, and, if not, by phone contact by the site. The patient's medical record may be reviewed to confirm patient's answers. This follow up will collect information on:

- Patient and graft survival;
- Liver graft related SAEs (6 months only);
- Liver graft related re-hospitalized after initial discharge, and, if yes, the primary reason/diagnosis for the hospitalization and the length of stay;
- Information will also be collected on any diagnosis of ischemic biliary complications and, if so, the method of diagnosis and treatment.

The 6 and 12-month follow-up will be collected within \pm 1 month of the designated period and will be recorded on the 6 and 12 month follow-up electronic form.

7.3.1.1. 24-Month Follow-up

At approximately 24 months post-transplant, the patient will be evaluated at an office visit if this is the institution's standard of care, and, if not, by phone contact by the site. The patient's medical record may be reviewed to confirm patient's answers. This follow up will collect information on:

- Patient and graft survival;
- Results of standard clinical practice or for cause liver biopsy will be collected (if applicable).

The 24 months follow-up will be collected within \pm 1 month of the designated period and will be recorded on the 24-month follow-up electronic form.

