8.2. Serious Adverse Events (SAEs)

An adverse event will be classified as serious if it meets any of the following criteria:

- Results in, leads to, or contributes to, a death;
- Is life-threatening;
- Results in permanent disability or incapacity (i.e., permanent impairment of a body function or permanent damage to a body structure);
- Requires in-patient hospitalization or prolongs hospitalization;
- Necessitates medical or surgical intervention to preclude a permanent disability or incapacity;
- Results in fetal distress, fetal death or a congenital anomaly/birth defect

All Liver graft-related SAEs will be followed until their resolution.

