11. TRANSPLANT CHARACTERISTICS AND RECIPIENT POST-TRANSPLANT HOSPITAL/ICU STAY

Transplant characteristics will be summarized using frequencies and percentages for categorical variables and descriptive statistics (n, mean, standard deviation, median, minimum, and maximum) for continuous variables.

The initial post- transplant Hospital/ICU stay duration and the re-admission Hospital/ICU stay duration will be summarized using descriptive statistics.

The initial post-transplant hospital stay is defined as the duration in days from ICU admission to post transplant hospitalization discharge.

The initial post-transplant ICU stay is defined as the duration in hours from ICU admission to initial ICU clinical order discharge. If the initial ICU clinical order discharge date and time are missing, the actual ICU discharge date and time will be substituted. If the time is missing, a value of 23:59 will be used.

These analyses will be performed for the PP, mITT and AT populations.

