In addition, the numbers and percentages of subjects experiencing at least one treatment-emergent adverse event (TEAE) in the following categories will be tabulated by treatment group: liver graft-related TEAEs, treatment-related (definitely or probably-related) TEAEs, serious TEAEs, and serious liver graft-related TEAEs. The number of treatment-emergent liver graft-related adverse events, treatment-emergent serious adverse events (within 30 days post-

transplant and overall), treatment-emergent serious liver graft-related adverse events (within 30 days post-transplant and overall), treatment-emergent adverse events resulting in study discontinuation, and treatment-emergent serious adverse events with an outcome of death (within 30 days post-transplant and overall) will be tabulated by system organ class and preferred term using MedDRA (Version 13.0 or higher). Liver graft-related TEAEs and liver graft-related serious TEAEs will also be tabulated at the event level by system organ class and preferred term and the relationship of the liver graft-related adverse event to the investigational treatment using counts and percentages. Similar analyses at the event level will be performed by the severity of the adverse event.

The adverse event analyses above will also be presented by subgroup.

An exploratory analysis of the frequency of non-ischemic biliary complications through 30 days post-liver transplantation per subject will be performed. This endpoint will be summarized by treatment group using descriptive statistics. For each treatment group, a 95% confidence interval for the mean based on the t-distribution will be presented. Also, a 95% confidence interval based on the t-distribution will be presented for the difference in means between the two treatments.

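### SAP 14 counts graft-related re-hospitalisation only from the 30-day visit, although the protocol item starts at initial discharge, so readmissions before day 30 are in neither count

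*SAP*

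**What the plan says.** Protocol 7.3.1 lists, among the items gathered at the 6- and 12-month contacts, "Liver graft related re-hospitalized after initial discharge, and, if yes, the primary reason/diagnosis for the hospitalization and the length of stay". The protocol synopsis lists the same item under Follow-up. In both places the period begins when the patient first leaves hospital.

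SAP 14, under Follow-up status, says what will be reported for the PP, mITT and AT populations. The first count is "The number of subjects with liver graft related re-hospitalization between the 30 day and 6 month follow-up visits". The second is the number "between the 6 month and 12 month follow-up visits will be summarized using counts and percentages". No third window is given.

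Two other parts of the SAP touch on readmissions. SAP 11 says that "the re-admission Hospital/ICU stay duration will be summarized using descriptive statistics", with no time limits and no restriction to graft-related causes. SAP 13 tabulates "treatment-emergent serious liver graft-related adverse events (within 30 days post-transplant and overall") by MedDRA term.

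**The concern.** The collection period and the reporting period do not match. Take a recipient discharged on day 12 and readmitted on day 20 because of the graft. This is a positive answer to the protocol item, but the readmission falls before the first SAP window opens. Followed as written, the SAP under-reports an item that the sites are asked to supply.

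What is at stake is the completeness of one descriptive result. Length of initial hospital stay is a listed endpoint, and a reader comparing stays between arms would naturally look at early graft-related returns beside it. The SAP's count leaves out the first part of the period at home.

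**Working it through.** The plan states no figure for this interval, so there is none to reproduce. The check has two steps.

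**1. Coverage, side by side**

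| Interval | Within the protocol item (7.3.1)? | Within a SAP 14 count? |
|---|---|---|
| Initial discharge to 30-day visit | Yes | No |
| 30-day visit to 6-month visit | Yes | Yes, first window |
| 6-month visit to 12-month visit | Yes | Yes, second window |

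The first row exists only for subjects discharged before the 30-day visit.

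**2. Length of the uncounted interval**

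Inputs:
- Start of the first SAP window: day 30 (SAP 14).
- Length of initial stay, *L*: the outcome table in Protocol 1.4.4 (row "Hospital Stay (days), median (range")) gives 12 days (range 6 to 34) with machine perfusion and 14 days (range 8 to 88) with cold storage. These come from a feasibility study of another perfusion device and are the only stays in the documents.
- Six months: taken as 183 days (assumption).

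Formulas: uncounted days = max(0, 30 − *L*); share of the time from discharge to month 6 = uncounted days / (183 − *L*).

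| *L* (days) | Uncounted days | Discharge to month 6 (days) | Share |
|---|---|---|---|
| 6 (shortest, perfusion) | 30 − 6 = 24 | 177 | 13.6% |
| 8 (shortest, cold storage) | 30 − 8 = 22 | 175 | 12.6% |
| 12 (median, perfusion) | 30 − 12 = 18 | 171 | 10.5% |
| 14 (median, cold storage) | 30 − 14 = 16 | 169 | 9.5% |
| 34 and 88 (longest) | 0 | 149 and 95 | 0% |

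At the two medians the difference between arms is 18 − 16 = 2 days, or about 1 percentage point of the time from discharge to month 6.

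These are shares of time, not of readmissions. Turning them into numbers of subjects would need a readmission rate by period, and the documents give none.

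**The case against.** The strongest reply is that the early readmissions are not lost. A graft-related event that meets the criterion "Requires in-patient hospitalization or prolongs hospitalization" is serious under Protocol 8.2, and SAP 13 tabulates serious graft-related events within 30 days. SAP 11 summarises the duration of readmissions in the same sentence as the initial stay, with no lower time limit. SAP 5.1 puts all collected data in the listings. This stands, and it rules out an inference a reader might draw, that these readmissions appear in no analysis. It does not supply the missing count. The SAE tables are organised by event term and do not identify readmissions, and the SAP 11 summary does not separate graft-related ones. The SAE route also has a weak point: one sentence of Protocol 8.5 ends recording at day 30 or discharge, whichever is earlier, while Protocol 8.1 and a later sentence of 8.5 carry graft-related events at least to the 30-day follow-up.

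A reader might also infer that the SAP narrowed a planned analysis without listing the change in SAP 3.5. The documents do not support that. Re-hospitalisation is a data-collection item in the protocol. It is absent from the endpoint lists and from the statistical section, so there was no protocol-specified analysis to change.

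A reader might further infer a bias between arms, because the arm that goes home earlier has more uncounted days. The mechanism is possible, but the cited medians imply only a 2-day difference and come from another device. Nor can a larger share of missed readmissions be claimed by assuming a higher rate soon after discharge, since the documents provide no such rate.

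Finally, the sponsor may intend the first window to hold everything reported on the 6-month form. In that case the data would be complete but the SAP's description of the window would be wrong, and the sentence would still need correcting.

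**Conclusion.** The point holds as a small reporting gap. The protocol item runs from initial discharge, both SAP 14 counts start at or after the 30-day visit, and no other planned analysis gives the number of subjects with a graft-related readmission between discharge and day 30. The uncounted interval is about 16 to 18 days per recipient at the cited medians, roughly 10% of the time from discharge to month 6. It is nil for stays of 30 days or more. These figures assume that stays in this trial resemble those of the cited study and that six months is 183 days.

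The number of subjects missed is unknown. The count is descriptive, carries no test, and sits among the additional evaluations, so no primary, secondary or safety conclusion depends on it.

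**What to change.** In SAP 14, Follow-up status, replace the first window with initial discharge to 6 months, keep 6 to 12 months as the second, and state that both are shown by treatment group. If readmission dates are recorded, split the first window at day 30 so that the early returns can be seen separately.

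The cost is one amended sentence and a small amount of extra tabulation. Moving the start of the window uses an item the protocol already collects and needs no new test. The split is conditional because Protocol 7.3.1 names the reason and the length of stay but not the date, and the case report forms are not reproduced in the protocol. The SAP's present start at the 30-day visit already requires some means of placing a readmission before or after that visit, so the sponsor should confirm what is held.
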